9.2.14 Investigational Medicinal Product Accountability

Records of GWP42003-P accountability will be maintained according to [Section 5.2.4](#).

GWP42003-P will be dispensed at Visit 1 (Day 1) and every scheduled visit thereafter (Visit 4 through Visit 14 [end of treatment/withdrawal visit]).

Caregivers will be asked to return all GWP42003-P (used and unused) at each relevant visit (Visits 4 through Visit 15 [end of taper]). The center will check the returned GWP42003-P against the expected usage. Any discrepancies will be discussed with the caregiver at the time of the visit and documented accordingly within the patient's source documents.

9.2.15 Adverse Events

All AEs (including SAEs) occurring during the trial will be reported on the running logs in the AE section of the eCRF. This includes all events from the time following screening (Visit 1) up to and including the post-trial follow-up visit (Visit 16), whether or not attributed to GWP42003-P and observed by the investigator or patient.

* For the patient's expected seizure types, these do not routinely require documentation as AEs. However, any worsening, including a change in the pattern or severity of seizures should be documented in the eCRF if deemed to meet the definition of an AE, in the investigator's opinion.

Study Code: GWND19002
EudraCT Number: 2019-001605-24
Clinical Protocol V2 18Dec19

Any AE that meets SAE criteria should still be reported as a SAE.

Serious adverse events must be reported to GW Pharmacovigilance Department (PVD) within 24 hours of discovery or notification of the event via recording in the eCRF.

Refer to [Section 12](#) for definitions, procedures, and further information on AE reporting.

Study Code: GWND19002
 EudraCT Number: 2019-001605-24
 Clinical Protocol V2 18Dec19

10 IMP WITHDRAWAL

In accordance with the Declaration of Helsinki⁷³ the International Council for Harmonisation (ICH) Harmonised Guideline: Integrated Addendum to ICH E6(R1): Guideline for Good Clinical Practice (GCP) E6(R2)⁷⁴ the FDA regulations relating to GCP and clinical trials^{75,76,77} the EU Clinical Trials Directive⁷⁸ the EU GCP Directive⁷⁹ and/or other applicable regulations, a patient has the right to withdraw from the trial at any time and for any reason, with no obligation to provide a reason and without prejudice to his/her future medical care by the physician or at the institution.

The patient must be withdrawn permanently discontinued from the trial if any of the following apply:

- Administrative decision by the investigator, GW, or a regulatory authority
- Pregnancy
- Protocol deviation that is considered to potentially compromise the safety of the patient
- Withdrawal of patient assent
- Withdrawal of parent(s)/legal representative consent
- ALT or AST > 3 × ULN with the appearance of fatigue, nausea, vomiting, right upper quadrant pain or tenderness, fever, rash, and/or eosinophilia (> 5%)
- ALT or AST > 8 × ULN
- ALT or AST > 5 × ULN for more than 2 weeks
- ALT or AST > 3 × ULN **and** (total bilirubin [TBL] > 2 × ULN **or** international normalized ratio [INR] > 1.5)

Note: Prior to withdrawal for the transaminase elevations noted above, the investigator may choose to confirm the transaminase elevations by repeating the following laboratory tests within 24 to 48 hours: ALT, AST, TBL, INR, % eosinophils, gamma-glutamyl transferase, alkaline phosphatase, and eosinophils. **Should the above transaminase elevation criteria be confirmed, the patient must be withdrawn from the trial. In cases where the transaminase elevation withdrawal criteria are not met or confirmed, the dose of IMP or a concomitant medication with known hepatotoxicity may be**

Study Code: GWND19002
EudraCT Number: 2019-001605-24
Clinical Protocol V2 18Dec19

reduced. Dose adjustments should be discussed with the GW medical monitor. The final decision regarding dose adjustments should be taken by the investigator.

- Lost to follow-up

The patient may also be withdrawn permanently from the trial for any of the following:

- Patient or caregiver noncompliance
- AE (including clinically significant laboratory result) that, in the opinion of the investigator, would compromise the continued safe participation of the patient in the trial
- Failure to meet the eligibility criteria
- Any evidence of the use of drugs of abuse or drug diversion
- Suicidal ideation or behavior during the treatment period

The patient should attend a withdrawal visit (Visit 14) as soon as possible after the decision is made to permanently discontinue GWP42003-P. Patients who discontinue the IMP should have their dose of IMP gradually reduced (10% each day) over a period of 10 days, beginning at the time the decision is made to discontinue (unless inadvisable due to an AE). Patients who discontinue the IMP and complete tapering of the IMP prior to the completion visit do not need to attend an End of Taper visit.

Should a patient request or decide to withdraw from the trial, all efforts must be made to complete and report the observations as thoroughly as possible up to the date of withdrawal. Patients withdrawing due to an AE should be followed up according to [Section 12.7](#). All information should be reported on the applicable eCRF pages. All assessments required at the withdrawal visit should be conducted, if possible. If the tapered dose is administered, patients should return for Visit 15 (End of taper), if possible. Wherever possible, a safety follow-up visit should take place 28 days from the date of last dose of IMP. If the withdrawing patient declines to give a reason for withdrawal of consent, the investigator must respect the patient's wishes.

Study Code: GWND19002
EudraCT Number: 2019-001605-24
Clinical Protocol V2 18Dec19

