4 EXPERIMENTAL PLAN

4.1 Trial Design

This is a multicenter, OLE trial for patients with RTT who have completed the randomized, double blind, placebo-controlled trial (GWND18064).

Entry to this OLE trial is recommended to be on the same day as Visit 9 of the randomized controlled trial (RCT), GWND18064; however, patients may enter the OLE up to the RCT follow-up visit (Visit 11).

All patients entering this OLE trial will begin dosing with 5 mg/kg/day GWP42003-P (2.5 mg/kg b.i.d.) on Day 1. Patients will be observed, and after 1 week, the dose may further be escalated, at the investigator's discretion, up to 15 mg/kg/day GWP42003-P (7.5 mg/kg b.i.d.) in weekly increments of 5 mg/kg/day (2.5 mg/kg b.i.d.).

Patients should then remain on a stable dose of GWP42003-P for the duration of the maintenance period of the trial (up to 104 weeks), with the option for doses to be decreased or increased to a maximum dose of 20 mg/kg/day (10 mg/kg b.i.d.) based on clinical response and tolerability, as deemed necessary by the investigator, until the optimal dose is found. Patients whose dose has been decreased can have their dose increased again if tolerability improves.

At the end of treatment (Visit 14 [Day 729]), the dose of GWP42003-P will be reduced over a 10-day taper period, and patients will enter the 4-week follow-up period.

If a patient permanently discontinues treatment at any point during the trial, GWP42003-P should be gradually reduced over 10 days (unless inadvisable due to an AE). The patient should attend a withdrawal visit (Visit 14) as soon as possible after the decision is made to permanently discontinue GWP42003-P. If applicable, the patient will taper GWP42003-P, attend the End of Taper visit (Visit 15), and then complete the 4-week follow-up period.

A schematic ([Figure 1-1](#)), presented at the end of [Section 1](#), depicts the overall trial design. More detailed information on treatment and trial procedures is provided in [Section 8](#) and [Section 9](#), respectively.

Study Code: GWND19002
EudraCT Number: 2019-001605-24
Clinical Protocol V2 18Dec19

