The Hospital Services Use Questionnaire will be completed via interview.

The Tanner Stage will be recorded (where appropriate).

The investigator will complete MBA-9, CGI-S, CGI-I, and suicidality assessment.

The investigator must assess adherence to the dosing schedule. All GWP42003-P (used and unused) will be collected, and a check of the returned GWP42003-P against usage should be made. Patients will receive sufficient GWP42003-P and a dosing schedule for the period until the next scheduled Visit.

Based on [Section 9.1.3](#), assessments may be performed at an unscheduled visit in the event of a safety concern, as deemed necessary by the investigator.

Visit 14 only: Patients will receive sufficient GWP42003-P for the 10-day taper period, as applicable. For patients who discontinue GWP42003-P early, the taper period should start at the time the decision is made to discontinue, unless tapering the dose of GWP42003-P is inadvisable (e.g., continued dosing is not possible due to an AE). For patients who discontinue GWP42003-P early, the decision on whether or not to taper GWP42003-P will be left to the investigator's clinical judgment.

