6.1 Statistical Definitions and Algorithms

6.1.1 Conventions for treatment/visit naming

In all tables, listings and figures, the treatment arms will be referred to and labelled as per [Table 2](#).

Table 2 Study treatments

Endpoint	RCT Treatment	Actual Treatment	Protocol/Annex	Treatment Label (Table column/Figure legend)	Sorting order in listings, column order in tables
All	Double-Blind Treatment GWP42003-P different dosing	GWP42003-P, at different dosing	Enrolled under Protocol	Double Blind Treatment: GWP42003-P Enrolled Under Protocol	1
All	Double-Blind Treatment GWP42003-P different dosing	GWP42003-P, at different dosing	Enrolled under Annex	Double Blind Treatment: GWP42003-P Enrolled Under Annex	2
All	Double-Blind Treatment Placebo different dosing	GWP42003-P, at different dosing	Enrolled under Protocol	Double Blind Treatment: Placebo Enrolled Under Protocol	3
All	Double-Blind Treatment Placebo different dosing	GWP42003-P, at different dosing	Enrolled under Annex	Double Blind Treatment: Placebo Enrolled Under Annex	4

In all tables, listings and figures, the study visits will be referred to and labelled as per [Table 3](#).

Table 3 Study Visits

Actual Visit	Visit Label
Baseline (last record before 1 st IMP administration during lead-in trial)	RCT Baseline
Baseline (Assessment at extension Visit 1)	OLE Baseline
Visit 1: Day 1	Day 1
Visit 2: Day 8 Telephone Call	Day 8 TC
Visit 3: Day 15 Telephone Call	Day 15 TC
Visit 4: Day 29	Day 29
Visit 5: Day 57	Day 57
Visit 6: Day 85	Day 85
Visit 7: Day 141	Day 141
Visit 8: Day 197	Day 197
Visit 9: Day 281	Day 281
Visit 10: Day 365	Day 365
Visit 12: Day 547	Day 547
Visit 14: Day 729 or withdrawal	End of Treatment
Visit 15: Day 739 (end of taper)	End of Taper
Visit 16: Day 767	Follow-up

No derivation will be used for visits; data will be tabulated and listed according to the visit it was recorded under in eCRF.

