7.4 Exposure and Compliance

IMP is to be administered twice daily (morning and evening). The first dose will be taken on Day 1 (Visit 1). The date of final dose in the treatment period will be recorded on the eCRF under DS

form. The date of final dose, for patients who enter the taper period, will be recorded on the eCRF at the end of taper visit under DS2 form. Total number of dosing days will be reported.

8. Efficacy Analysis

The efficacy analyses will use the safety analysis set. No formal hypothesis testing will be carried out for this study. Statistical analysis will be descriptive.

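### Protocol Section 10 gives conflicting End of Taper instructions for patients who stop early, and the SAP's End of Treatment row can pool on-drug with reduced-dose or off-drug values

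*Protocol*

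**What the plan says.** All protocol references are to V2.

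- **Protocol Section 10, paragraph on stopping the drug.** The dose is to be "gradually reduced (10% each day) over a period of 10 days, beginning at the time the decision is made to discontinue", unless an adverse event makes that inadvisable. Visit 14 follows the decision as soon as possible. Patients who discontinue and "complete tapering of the IMP prior to the completion visit do not need to attend an End of Taper visit".
- **Protocol Section 10, next paragraph, on withdrawing from the trial.** "If the tapered dose is administered, patients should return for Visit 15 (End of taper), if possible".
- **Protocol Section 4.1, with the synopsis to the same effect.** Where a taper applies, "the patient will taper GWP42003-P, attend the End of Taper visit (Visit 15), and then complete the 4-week follow-up period". Neither place contains an exemption.
- **Protocol Section 9.1.1.6, Visit 14 only.** For early discontinuers "the taper period should start at the time the decision is made to discontinue", and the taper supply is handed out at Visit 14.
- **SAP Section 6.1.1, Table 3.** One label, End of Treatment, covers "Visit 14: Day 729 or withdrawal". The text under the table says that no visit derivation is used and that data stay under the visit recorded in the eCRF.
- **SAP Section 7.4.** The last dose of the treatment period goes on the DS form. For patients who taper, the final dose date "will be recorded on the eCRF at the end of taper visit under DS2 form".

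**The concern.** There are two linked problems.

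The first is the visit rule. A patient who withdraws early and has finished the taper falls under both the exemption and the instruction to return. Which one a site applies depends on what it takes the completion visit to be. Visit 15 is where post-taper vital signs and suicidality are scheduled, where the taper supply comes back, and where the final taper-dose date is recorded. Visit 16 is timed from the last dose, so an uncertain date also blurs the follow-up.

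The second comes from timing and labelling and would remain if Section 10 were reworded. Dose reduction begins at the decision, while the withdrawal visit may come some days later. Its values still go into the same row as those of patients assessed on their maintenance dose at Day 729. Change from the RCT baseline to end of treatment is a planned primary safety output for vital signs and IGF-1 (Protocol 13.6.2.3) and for laboratory data (Protocol 13.6.2.4), and SAP 9.3.5 plots it for IGF-1.

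**Working it through.** **1. The schedule reproduces.** Visit 14 is Day 729. Adding the 10-day taper gives 729 + 10 = 739, the stated day of Visit 15. Adding 28 days of follow-up gives 739 + 28 = 767, the stated day of Visit 16.

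**2. Two readings of the completion visit.** V2 does not define it.

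- *Read as Day 729.* The Definition of Terms contrasts completing the treatment period with withdrawal, and note b of Appendix 1 contrasts completing with withdrawing, so a site could read it this way. Since Visit 14 dispenses the taper supply, it would normally come before the taper ends. Skipping Visit 15 then loses the items in Protocol 9.1.1.10: required vital signs, suicidality, adherence review and drug return, plus examination, ECG and laboratory tests where clinically indicated. The DS2 date is lost with them. Visit 16 is a telephone call and replaces none of these assessments. Adverse events continue to Visit 16 (Protocol 9.2.15), and follow-up four weeks after the last dose is required for everyone (Appendix 1, note c).
- *Read as Visit 14.* The exemption can apply only if Visit 14 falls after the taper has ended, about 9 to 10 days or more after the decision. That visit collects vital signs, ECG, laboratory tests, suicidality and returned drug (Protocol 9.1.1.6), which is more than Visit 15 requires. Post-taper data are then present, and what is missing is an end value on drug.

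Protocol V1 shows where the wording comes from. There the exemption followed a sentence keeping discontinuers in the trial with visits per protocol. V2 drops that sentence and keeps the exemption.

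**3. Dose at a delayed Visit 14.** Let k be the days from decision to Visit 14. The documents give no limit on k, so the values below are assumptions. At 10% of the starting dose per day, the dose remaining is 100 − 10(k + 1)% if the first cut is on the decision day, or 100 − 10k% if it is the next day, with a floor of zero.

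| k (days) | First cut on decision day | First cut next day |
|---|---|---|
| 0 | 90% | 100% |
| 3 | 60% | 70% |
| 5 | 40% | 50% |
| 7 | 20% | 30% |
| 10 | 0% | 0% |

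**4. Effect on the summary.** If a fraction f of the End of Treatment row is measured after the taper began, the pooled mean change is (1 − f) × on-drug change + f × later change. Where an effect recedes as the dose falls, this dilutes the on-drug change. No withdrawal rate or distribution of delays is given, so f cannot be computed. By-visit ECG summaries (SAP 9.3.2) also contain this row. IGF-1 is most exposed, because after Visit 1 it is scheduled only at Visits 8, 10 and 14: a patient who stops before Day 197 has the withdrawal visit as her only scheduled post-baseline value.

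**The case against.** The other side has several fair points.

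- The two Section 10 statements sit in adjacent paragraphs, the exemption is conditional, and the return is asked for only where possible. They overlap for some patients and are not flat opposites. This stands. It does not remove the overlap, or the conflict with Section 4.1 and the synopsis.
- With the V1 sentence gone, Visit 14 is arguably the more natural meaning of the completion visit, and then little post-taper information is lost. This stands for that reading, but the text does not exclude the other.
- Dispensing the taper supply at Visit 14 suggests that Visit 14 was meant to open the taper. That is probably the intent, but no limit enforces it.
- A reader might infer that pooling hides on-drug abnormalities. The SAP does not support that. Laboratory values, vital signs and ECG are summarized at every visit, ALT/AST thresholds count if met at any time after baseline (SAP 9.2.1), and vital-sign and ECG flags count any post-baseline value (SAP 9.3.1, 9.3.2). Dilution of the end-of-treatment change is the supportable claim.
- SAP 6.1.8.4 computes dosing days from the Study Outcome form, so that summary does not depend on the DS2 date.

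**Conclusion.** Both parts hold and should be fixed. The visit instructions conflict for early discontinuers who taper. The loss of post-taper data depends on a site reading the completion visit as Day 729, or applying the exemption to a patient seen at Visit 14 before the taper ends. The mixing of dose levels in the End of Treatment row follows from the timing and labelling rules under either reading. Its size is unknown: the percentages in the table rest on assumed delays, and dilution assumes that the effect recedes with dose.

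Two stronger conclusions are tempting and not supported. A reader might note that anyone stopping by Day 719 finishes a 10-day taper by Day 729, and that 719/729 = 98.6%, and infer that nearly all patients are excused. That figure is a share of calendar days, on one of the two readings, and not a proportion of patients. A reader might also take the statement in SAP Section 1 that the extension is stopped prematurely to mean that most patients qualify. SAP 9.5 says that those who enter complete the trial per protocol and annex.

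**What to change.** **Protocol.** The sponsor should reconcile the two paragraphs of Section 10 with the synopsis, Section 4.1 and Section 9.1.1.6, and define the completion visit, so that one visit and data-collection rule applies to patients who taper early. Which rule that is remains the sponsor's decision; no taper, dose or stopping rule is proposed here.

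**SAP.** In Table 3 and Sections 9.2 and 9.3, compare the date of each Visit 14 assessment with the treatment-period last-dose date on the DS form. Present values taken after that date in their own row, or flag them, and keep the remaining values as on-treatment End of Treatment. State how a visit on the day after the last full dose is classed, so that completers who took it the evening before are not misplaced. This assumes that the DS date is the last dose before the taper, as SAP 7.4 implies.

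**Cost.** A wording change in the protocol and one derivation from dates already collected. The SAP part needs no extra visit. The on-treatment row will have a smaller n and will tilt towards completers, so the pooled row should be shown beside it.

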11 URGENT SAFETY MEASURES

The sponsor and investigator may take appropriate urgent safety measures in order to protect the patients of a clinical trial against any immediate hazard to their health or safety. If such measures are taken by the investigator, they must notify GW immediately or at least within 24 hours of awareness. GW will report urgent safety measures to regulatory authorities by telephone within 24 hours of awareness, wherever possible, and will provide a written report to the regulatory authorities and IRB/IEC within 3 days.

Study Code: GWND19002
EudraCT Number: 2019-001605-24
Clinical Protocol V2 18Dec19

12 ADVERSE EVENT REPORTING

12.1 Definitions

12.1.1 Adverse Event

For the purposes of this trial, an AE is defined as follows:

Any new unfavorable/unintended signs/symptoms (including abnormal laboratory findings when relevant) or diagnosis or worsening of a pre-existing condition that occurs at any point up to the post-treatment, final safety follow-up visit (Visit 16), which may or may not be considered to be related to GWP42003-P. Any event that is the result of a trial procedure must be recorded as an AE.

Surgical/Investigational procedures are not AEs. The medical reason for the procedure is the AE. Elective hospitalizations for pretrial existing conditions or elective procedures are not AEs. The exception may be if the patient has an AE during hospitalization that prolongs the scheduled hospital stay, in which case it would be considered an SAE (refer to [Section 12.2](#)).

If reporting a fatal event, the SAE term should be the underlying cause of death (e.g., disease or medical condition leading to death).

12.1.2 Investigator

The term “investigator” refers to the trial principal investigator (PI) or a formally delegated trial physician.

12.2 Serious Adverse Events

During clinical investigations, AEs may occur, which if suspected to be GWP42003-P-related, might be significant enough to lead to important changes in the way GWP42003-P is developed (e.g., change in dose, population, monitoring need, consent/assent forms). This is particularly true for events that threaten life or function. Such SAEs will be reported promptly to regulatory authorities, applicable IRBs/IECs, and investigators (expedited reporting) by GW.

An AE must only be classed as serious, i.e., an SAE, when the event falls into one of the following criteria:

- Results in death
- Is life threatening^{*}

Study Code: GWND19002
EudraCT Number: 2019-001605-24
Clinical Protocol V2 18Dec19

- Requires inpatient hospitalization or prolongation of existing hospitalization
- Results in persistent or significant disability/incapacity
- Is a congenital anomaly/birth defect
- Is medically significant**

* The term “life threatening” in the definition of “serious” refers to an event in which the patient was at risk of death at the time of the event; it does not refer to an event that, hypothetically, might have caused death if it were more severe.

** Medical and scientific judgment should be exercised in deciding whether SAE reporting is appropriate in other situations. Important medical events may not be immediately life threatening or result in death or hospitalization but may jeopardize the patient or may require intervention to prevent one of the other outcomes listed in the definition above. These should also usually be considered serious. Examples of such events are intensive treatment in an emergency room or at home for allergic bronchospasm, blood dyscrasias or convulsions that do not result in hospitalization, or development of drug dependency or use of drugs of abuse.

